2.1 Background and rationale

This randomised controlled feasibility study was run to pilot a patient-engagement tool (PET) developed to increase COVID-19 and Flu vaccination uptake in underserved at-risk populations including migrants and persons with ethnic minority (EM) backgrounds in East London. The rationale was to assess acceptability and feasibility of the intervention: results will be used to plan a larger study to evaluate effectiveness.

2.2 Objectives

The primary objectives are to determine the feasibility, design, and implementation plan for a subsequent randomised controlled trial to evaluate the effectiveness of the PET for increasing uptake of COVID-19 and Flu vaccination.

The secondary objectives are to determine (i) an estimate of COVID-19 and Flu vaccination uptake, its variation by population group, and other parameters to design a subsequent randomised controlled trial; (ii) the feasibility and practicality of implementing the PET; and (iii) the appropriate level of support needed for health care providers at site-level to ensure successful implementation of the PET and to identify supporting activities needed to implement interventions for COVID-19 and Flu vaccinations.

3 Study Methods

3.1 Trial design

The PET was designed in qualitative work packages that preceded the feasibility trial. Eligible patients from six general practitioner (GP) practices from Tower Hamlets and Newham were individually randomised 1:1 to the intervention (PET) or control (routine care) during the study. The Appt-Health workflow tool was used, but patients in the control group did not receive additional (individual level) interventions outside routine; however some “cluster-level” interventions were used including posters in surgeries. Letters were used to invite patients with no device to receive SMS invitation for flu vaccination.

To enable a comparison of the intervention to a control group at a practice level, we randomised GPs after they were recruited to the study. n=6 practices were randomised 1:1 to two groups of size n=3 vs. n=3. During a first study period, the first group of n=3 GPs received training, activation of the software, and patients were randomised. This happened for the second group of GPs in a subsequent study period.

A cluster-level analysis will use data from the first period in all n=6 GPs. The individual-randomisation comparison will use data from all GPs, with the second group contributing data from the second period only.

3.2 Randomisation

The practices were randomised in one block by the statistician, independent from the trial team. Individuals within each GP were randomised using simple randomisation in the practice software (reference: <https://learn.microsoft.com/en-us/dotnet/api/system.random?view=net-8.0>). This was done on the same day or shortly after the eligible list was determined. The randomised allocation was concealed to staff; patients were not told about arm beyond option to opt out – where they got the study information from a website.

3.3 Sample size

The sample size used was chosen based on calculations reported in the protocol (reference: COVID-19 vaccine uptake amongst underserved populations in East London protocol V5.0) and justified based on uptake.

3.4 Framework

- Primary analysis on uptake will report 95% CI, with no p-values to test superiority because this is a feasibility study that is not powered on superiority.
- Secondary analysis on other outcomes will use descriptive analysis.

3.5 Timing of final analysis

Final analysis will be done by September 2024 using a database with updated follow up (to >180 days for all).

4 Statistical Principals

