6.1 Outcome definitions

6.1.1 Primary outcome

The primary outcome is vaccination uptake in patients individually randomised. This will be measured as the number (percent) of relevant SNOMED codes in eligible patients. Uptake will be measured from the time that the eligible group in each practice is identified (and randomised) until 6 months follow-up (>180 days since randomisation).

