6.1.2 Secondary outcomes

1. Vaccination uptake in patients after 3- and 9-months follow-up (>90 and >270 days). This will be measured as the number (percent) of relevant SNOMED codes in eligible patients identified during the period.
2. Mean vaccination rate after 3-, 6- and 9-months follow-up. This will be measured as the number of patients vaccinated divided by the follow-up time. Time is defined as time from randomisation until the earliest of vaccination, leaving the GP, withdrawal the consent of use of data, or death.
3. Acceptability of the intervention
 - a. To patients: Proportion of patients randomised to the intervention who engage with the PET and / or linked patient resources, as determined by user statistics logged on the software for
 - i. The SMS messaging tool (number of SMS sent)
 - ii. Number (percent) of patients who view the linked patient awareness resources
 - iii. Usage of the patient work list tool
 - b. To staff: Number and proportion of eligible patients randomised to the intervention processed using the patient work list tool
4. Feasibility of the intervention and randomisation
 - a. Number and proportion of eligible patients randomised
 - b. Clinical capacity: number of slots available for vaccination bookings for each GP surgery and each day, by appointment time
5. Feasibility of the study design for a subsequent trial

- a. Number and proportion of patients with all inclusion / exclusion data available on the electronic health records
- b. Number and proportion of patients eligible for the intervention
- c. Number and proportion of patients randomised who are sent material from the intervention (letter / sms)
- d. Number and proportion of patients eligible by vaccination status (none, first, second, with booster or without booster)
- e. Number and proportion of patients who opt out for their data to be used or withdraw from the study
- f. Number and proportion of patients who consent for further questionnaires
- g. Number and proportion of patients who are booked for a vaccination appointment
- h. Number and proportion of patients who are categorised a “failed encounter” (not booked, no more action taken)

This list only includes quantitative endpoints in the protocol. There will be additional qualitative analysis of other points in the protocol.

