6.2 Timing of outcome assessments

6.2.1 Timing of primary endpoint

Consent and uptake to vaccination will be determined based on patients having the vaccination done. The window to record this will be from the time that the eligible patient in each practice is identified and randomised until 6 months (180 days) follow-up. Follow begins when practices became live, and is the same time for each patient included from the same GP.

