6.2.2 Timing of secondary endpoints

The number of patients having the vaccination done since randomisation until 3- (90 days) and 9-months (210 days) follow-up.

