6.3.5 Exploratory analysis

We will explore vaccination uptake in patients after 9-months follow-up. We will explore the cluster-randomised component of this study. The population of analysis is those identified as eligible in both groups in the first study period, from the same calendar time. Analysis of uptake will take clustering in the design into account by using generalised linear models with (normal) random intercepts, and the model will also be used to obtain an estimate of the intra-class correlation coefficient. There are several methods to analyse cluster randomised trial data and we will also explore different models and assumptions in order to propose methods for the larger trial.

We will also explore whether a per-protocol analysis would be possible, by determining feasibility to define compliance / contamination from individual randomised allocation using process data. We will explore an analysis that makes use of the comparison between period 1 and period 2 in the n=3 GPs who are activated in the second period. This analysis may be

confounded by temporal effects so is treated as an exploratory analysis.

We will also adjust estimates using additional variables ethnicity and deprivation as an exploratory analysis.

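### The final database is guaranteed only >180 days of follow-up, which does not secure the 9-month outcomes, and no rule covers practices that fall short

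*SAP*

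**What the plan says.** Section 3.5 describes the final analysis and its database: "Final analysis will be done by September 2024 using a database with updated follow up (to >180 days for all". The primary outcome in section 6.1.1 runs "until 6 months follow-up (>180 days since randomisation", so the database floor and the primary window agree.

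Section 6.1.2 adds two secondary outcomes that reach further: "Vaccination uptake in patients after 3- and 9-months follow-up (>90 and >270 days" and "Mean vaccination rate after 3-, 6- and 9-months follow-up". Section 6.2.2 restates the uptake windows differently: "The number of patients having the vaccination done since randomisation until 3- (90 days) and 9-months (210 days) follow-up". Section 6.3.5 lists the same quantity again as exploratory: "We will explore vaccination uptake in patients after 9-months follow-up".

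On follow-up, section 3.1 says that the six practices were activated in two groups of three, the second in a later period. Section 6.2.1 adds: "Follow begins when practices became live, and is the same time for each patient included from the same GP". For the rate, section 6.1.2 says: "Time is defined as time from randomisation until the earliest of vaccination, leaving the GP, withdrawal the consent of use of data, or death". Sections 4.3.1 and 6.3.3 together put outcome summaries on an intention-to-treat basis, meaning everyone randomised.

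**The concern.** Uptake by 9 months is planned as a simple proportion. A simple proportion is valid only if everyone in the denominator has been observed for the whole window. The only follow-up the SAP promises is the 6-month minimum, and staggered activation gives the second group of practices the shorter follow-up. If some of those practices had passed 180 but not 270 days at the cut, the pooled 9-month figure would mix 9-month uptake in early practices with uptake at some earlier time in late ones.

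The study exists to supply uptake estimates and other design parameters for a larger trial (section 2.2). A small rise between 6 and 9 months could then be real or a product of the data cut, and the pooled figure alone would not show which. Section 2.2 does not name follow-up length among those parameters, so its use for that choice is a plausible consequence and not a stated one.

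**Working it through.** **1. Guaranteed follow-up against required follow-up**, in whole days, reading >180 as at least 181 and >270 as at least 271:

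- 3 months (>90 days) and 6 months (>180 days): covered by section 3.5.
- 9 months under section 6.1.2: 271 − 181 = 90 days not guaranteed.
- 9 months under section 6.2.2: 210 − 181 = 29 days not guaranteed (30 if read as >210).

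So the floor misses the 9-month window under either of the SAP's two definitions.

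**2. Go-live dates that would create the problem.** The SAP gives neither go-live dates nor a cut date. Taking the two ends of September 2024 as assumed cuts:

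| Assumed cut | Latest go-live for >180 days | Latest go-live for >270 days | Go-live range that meets 3.5 but not 9 months |
|---|---|---|---|
| 1 Sep 2024 | 4 Mar 2024 | 5 Dec 2023 | 6 Dec 2023 to 4 Mar 2024 |
| 30 Sep 2024 | 2 Apr 2024 | 3 Jan 2024 | 4 Jan to 2 Apr 2024 |

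An earlier cut, which section 3.5 also allows, moves these dates back by the same number of days.

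**3. Treatment of short follow-up.** Sections 4.3.1 and 6.3.3 keep all randomised patients in the denominator. Section 6.1.2 counts vaccination codes and states no exclusion for patients short of the window. Section 6.4, on missing data, does not mention incomplete follow-up. Followed literally, an unvaccinated patient with 200 days of follow-up enters the 9-month percentage as unvaccinated.

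**4. Size.** Let s be the share of patients in practices short of 270 days, U9 their true 9-month uptake, and U(t) their uptake at their actual follow-up t. Then

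shortfall in pooled uptake = s × (U9 − U(t)), at most s × (U9 − U6),

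with the maximum reached when they have only about 180 days. The SAP gives no value for any of these terms. As an illustration only, take U6 = 30% in all practices, the same U9 in all practices, and s = 0.33 or 0.50:

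| Assumed U9 | Gain U9 − U6 | Shortfall, s = 0.33 | Shortfall, s = 0.50 |
|---|---|---|---|
| 32% | 2 points | 0.7 points | 1.0 points |
| 35% | 5 points | 1.7 points | 2.5 points |
| 41.4% (constant rate: 1 − 0.70^1.5) | 11.4 points | 3.8 points | 5.7 points |

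The last row needs vaccination to continue at a constant rate for nine months. Section 5.2 defines eligibility by seasonal vaccination, so that row is an extreme. If s = 0, the shortfall is zero.

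**5. The rate.** Its denominator is person-time, so unequal follow-up does not pull it down as it does the proportion. Its gap is one of definition. A patient who stays registered and alive, does not withdraw and is never vaccinated meets none of the listed end points. The SAP names no end at the data cut or at the 3-, 6- or 9-month window. That holds whatever the calendar dates.

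**The case against.** The strongest reply is that >180 days is a floor chosen to match the primary window. Every practice may have passed 270 days by the cut. This stands: a reader might infer that the later practices will be short at 9 months, but without go-live or cut dates the SAP supports only that they could be.

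A second reply is that >270 days in section 6.1.2 can itself be read as a condition on follow-up attained, since sections 3.5 and 6.1.1 use the same form. That reading is possible, but no rule says that patients or practices short of it are left out, and the intention-to-treat summaries point the other way.

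Third, the harm is limited, and this stands too. Section 6.3.4 breaks primary and secondary endpoints down by GP, and section 5.3 puts each site's study period in the flow diagram, so a mixture could be noticed. Secondary outcomes are descriptive (section 3.4).

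Two further inferences should be resisted:

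- That short follow-up would unbalance the arms. Patients were randomised within practice and share one follow-up time there (section 6.2.1), so arms within a practice are observed equally long.
- That the rate would also be biased low. If vaccination slows late in the season, shorter follow-up would raise the average rate.

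**Conclusion.** The concern holds as a gap in the plan, not as a demonstrated error in the result. The guaranteed follow-up is up to 90 days short of the 9-month window in section 6.1.2 and about 30 days short of the one in section 6.2.2, and nothing says how practices short of it are handled. If any practice falls in that gap, pooled 9-month uptake as planned is too low by at most s × (U9 − U6).

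The amount cannot be derived from the SAP. The illustrations run from 0.7 to 2.5 points for modest late gains and up to 5.7 points under a constant rate, all on assumed inputs. Two parts do not depend on dates: the rate lacks a stated end of person-time, and 9-month uptake carries two definitions (270 and 210 days) and two statuses (secondary and exploratory).

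The point is of moderate weight. The 6-month primary outcome is fully covered, and the affected results are descriptive.

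**What to change.** In sections 3.5 and 6.1.2, state the data-cut date and adopt one of these:

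- require >270 days for all practices before the final analysis;
- compute 9-month uptake only in practices with >270 days, name them, and show 6-month uptake in the same practices beside it;
- estimate 9-month uptake from time-to-vaccination curves censored at the cut.

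The second option keeps the arms comparable, because follow-up is common within a practice.

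For the rate, add that person-time also ends at the earlier of the data cut and the relevant 3-, 6- or 9-month window. Reconcile 270 with 210 days between sections 6.1.2 and 6.2.2, and list 9-month uptake once, as secondary or as exploratory.

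The cost is SAP wording. If all practices had in fact passed 270 days, saying so in section 3.5 closes the follow-up gap without further change. If they had not, waiting would delay the final analysis, while restricting to eligible practices would rest the 9-month result on fewer practices with a wider confidence interval.

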4.1 Confidence intervals and P values

For the primary outcomes two-sided 95% confidence intervals will be used for uptake in each arm, and for the comparison between arms. For secondary outcomes confidence intervals (CIs) will be presented with no adjustment for multiplicity. For all other outcome point estimates, 95%CIs will be reported and no a priori statistical significance or decisions based on cut points for p-values will be used.

4.2 Adherence and Protocol deviations

The main protocol deviations to be summarised are patients who were randomised but did not meet inclusion / exclusion criteria (we expect this to be zero, as eligibility was determined prior to randomisation). The number and percentage of patients in each arm with this type of protocol deviation will be reported, as well as the number (%) of all other protocol deviations per patient; and in total.

4.3 Analysis populations

4.3.1 Intention to treat

This is all patients randomised, including withdrawals, with comparisons on the basis of randomised allocation.

4.3.2 Per-protocol population

This is all patients who consent, are randomised, do not withdraw, and receive the intended intervention.

5 Trial Population

5.1 Screening data

Public data on GP practice profiles will be collated (Fingertips), as will be the number of potential participants invited and opted out.

5.2 Eligibility

Eligible participants will be those aged 18 years or older and registered at study site (GP surgery), who are eligible for COVID-19 vaccination (i.e., are aged 75 years old or over, or live

in a care home for older adults, or are aged 6 months old or over and have a weakened immune system and have not received COVID-19 vaccination that season) or Flu vaccination (i.e., are aged 65 or over, or have certain long-term health conditions, or are pregnant, or live in a care home, or are the main carer for an older or disabled person or receive a carer's allowance, or live with someone who has a weakened immune system and those who have not received the seasonal Flu vaccination). This study is designed for underserved populations in East London, the underserved population group is defined as (i) non-white ethnicity; or (ii) resident in a postcode in the bottom 20% of index of multiple deprivation; or (iii) those receiving little or no income. Underserved population will be identified using (i) and (ii) as it is unable to assess (iii) in practice.

Patients were ineligible if they were unable or unwilling to consent (including those who did not consent to text messaging; those who opted out from taking part in research studies; and those who opted out from data sharing with NHS Digital national opt out).

5.3 Recruitment

Information to be included in the CONSORT flow diagram:

- The location (site),
- Vaccination group (COVID-19, Flu),
- Invitation method (COVID-19: sms; Flu: sms and letter), and
- Study period of each site.

Information on patients assessed for eligibility will not be recorded.

5.4 Withdrawal/ Follow-up

The number of withdrawals is expected to be very small. The number of participants who withdraw from the study after (opt-out) consent will be reported, and thereafter withdrawals separated by randomised allocation on an intention-to-treat basis. Timings of withdrawal will be the number (reporting only categories >0):

1. Between enrolment to 3 months follow-up, after receiving vaccination
2. Between enrolment to 3 months follow-up, not vaccinated
3. Between 3-6 months, after receiving vaccination
4. Between 3-6 months, not vaccinated
5. Between 6 months to end of study, after receiving vaccination
6. Between 6 months to end of study, not vaccinated

5.5 Baseline patient characteristics

The following baseline characteristics will be summarised:

- Demographics
 - Age (y)
 - Sex (male/female)
 - Ethnicity (all groups with >5 participants separately, <5 will be grouped as others)

- Index of multiple deprivation (decile)
- Comorbidities (yes/no)
- Indication for vaccination (recommended for COVID, FLU, or both)
- GP

Characteristics will be presented on an intention to treat basis. Categorical data will be shown with number and percentage. Continuous data will be shown as median and inter-quartile range, range. Some numerical data will be categorised (age, index of multiple deprivation, income) and shown as continuous and categorical summaries using cut points defined in this SAP. No p-values will be presented to compare baseline characteristics between the two groups. The summaries will be presented using a table (see appendix for dummy table).

6 Analysis

6.1 Outcome definitions

6.1.1 Primary outcome

The primary outcome is vaccination uptake in patients individually randomised. This will be measured as the number (percent) of relevant SNOMED codes in eligible patients. Uptake will be measured from the time that the eligible group in each practice is identified (and randomised) until 6 months follow-up (>180 days since randomisation).

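### Eligibility is tied to a vaccination season but uptake is not, so a later-season dose inside the follow-up window would count as success

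*SAP*

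**What the plan says.** SAP 5.2 (Eligibility) defines the population by season. For COVID-19 the patient must "have not received COVID-19 vaccination that season"; for flu the list is "those who have not received the seasonal Flu vaccination".

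SAP 6.1.1 (Primary outcome) defines uptake by codes: "This will be measured as the number (percent) of relevant SNOMED codes in eligible patients". The period is "Uptake will be measured from the time that the eligible group in each practice is identified (and randomised) until 6 months follow-up". SAP 6.2.1 restates the window as "identified and randomised until 6 months (180 days) follow-up" and starts the clock at each practice's go-live. SAP 6.1.2, item 1, extends the same code-based definition to other horizons: "Vaccination uptake in patients after 3- and 9-months follow-up (>90 and >270 days".

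SAP 3.1 activates three practices in a first period and three in a later one, without dates. SAP 3.5 places the final analysis by September 2024, with more than 180 days of follow-up for everyone. SAP 2.2 makes the estimate of uptake, and its variation between groups, an objective in its own right, to be used in designing the next trial.

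**The concern.** The event that makes a patient eligible (no dose this season) and the event that counts as success (any relevant dose within so many days) are not the same kind of event. They coincide only while the window stays inside the season in which the eligible list was drawn up. Once it passes into another season, success can mean responding to a different campaign.

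Two results would suffer. The uptake level, which is a deliverable for planning the larger trial, would be too high as a measure of uptake of the dose offered. The PET contrast would be diluted by doses that arise in both arms from a new campaign. Uptake by practice (SAP 6.3.4) could also mix different seasons and so look like practice heterogeneity.

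**Working it through.** The SAP states no uptake rate, effect size or season date, so there is no figure of its own to reproduce. Two checks are possible.

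**1. Can the window reach a later season?**

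Inputs from the SAP: a 180-day primary window from go-live (6.2.1); a 9-month window of 270 days (6.1.2; section 6.2.2 gives 210 for the same time point); analysis by September 2024 with more than 180 days for all (3.5). I take 1 and 30 September 2024 as the data cut. An earlier cut would shorten the reach.

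- Latest go-live = cut − 181 days: 4 March 2024 (cut 1 September) or 2 April 2024 (cut 30 September).
- The window crosses a boundary S if go-live falls before S but later than S − 180 days.

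The boundaries below are assumptions chosen to show the range.

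| Assumed boundary S | 180-day window crosses if live after | Largest overlap, cut 1 Sept | Largest overlap, cut 30 Sept |
|---|---|---|---|
| 1 April 2024 | 4 October 2023 | 152 days (live 4 March, ends 31 August) | 179 days (live 31 March, ends 27 September) |
| 1 September 2024 | 5 March 2024 | 0 | 28 days (live 2 April, ends 29 September) |
| 1 October 2024 | 4 April 2024 | 0 | 0 |

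The 270-day window crosses the same boundaries for go-live after 6 July 2023, 6 December 2023 and 5 January 2024 respectively. For 1 October this is only nominal: a database cut by 30 September contains no dose given from that date.

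**2. What would crossing do to the estimates?**

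Let p be in-season uptake in an arm, and q the chance that a patient unvaccinated in season takes a later-season dose inside the window, assumed equal in both arms.

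- Reported uptake = p + (1 − p)q.
- Reported risk difference = (true difference) × (1 − q).
- Reported odds ratio = (odds in PET arm + q) / (odds in control arm + q), which moves towards 1 as q rises.

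With assumed p of 20% (control) and 25% (PET), the odds are 0.250 and 0.333:

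| q (assumed) | Control | PET | Difference, points | Odds ratio |
|---|---|---|---|---|
| 0 | 20.0% | 25.0% | 5.00 | 1.33 |
| 5% | 24.0% | 28.75% | 4.75 | 1.28 |
| 10% | 28.0% | 32.5% | 4.50 | 1.24 |
| 20% | 36.0% | 40.0% | 4.00 | 1.19 |
| 30% | 44.0% | 47.5% | 3.50 | 1.15 |

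The level moves more than the contrast: at q = 10%, control uptake rises by 8 points while the difference shrinks by 0.5.

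**The case against.** Much of the case on the other side stands.

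- **It may not happen.** No go-live or season dates are given, and the September 2024 analysis date limits how far any window can reach. With a boundary of 1 October 2024, the primary outcome is untouched. This stands, and it is why the size is a range that starts at none.
- **The code may already be season-specific.** The word relevant in 6.1.1 could be meant that way, and a code list may be in the protocol, which is not shown. The missing list is therefore not the complaint. What remains is that the SAP's own outcome rule is a day count and does not state the restriction. Also, *that season* in 5.2 may grammatically attach only to the last COVID-19 criterion; the flu criterion is seasonal either way.
- **The arm comparison is protected from calendar bias.** Randomisation is 1:1 within practice (3.1, 3.2), the model adjusts for GP (6.3.2), and no superiority test is planned (3.4). This stands: later-season doses do not by themselves favour one arm. Adjustment for GP does not, however, correct the uptake level or undo the dilution within a practice.
- **There are partial safeguards.** Uptake at 3 months is the least exposed horizon, and results are shown by GP. Neither separates the two kinds of dose at 6 months.
- **Truncating follow-up at season end has its own cost.** It would give practices unequal windows. This stands and shapes the fix.

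A reader might go further and infer that the problem is worse in the later-activated practices. Section 6.3.1 gives some support: it drops second-group patients vaccinated in the first period, which suggests that both periods shared a season. But the SAP does not say so. If the second period opened with a new season, the direction vanishes or reverses. If the wording "until 6 months follow-up (>180 days since randomisation" means follow-up to a common data cut, every practice's window ends on the same date.

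**Conclusion.** The mismatch is in the text: eligibility is season-specific, the outcome window is not, and as written a later-season dose inside the window counts as uptake. This does not depend on any assumed figure.

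Its practical size is unknown from the SAP. Depending on the assumed boundary and data cut, the part of the 180-day window lying in a later season runs from 0 to 179 days. Where crossing occurs, reported uptake rises in both arms. The contrast moves towards the null provided later-season doses are equally likely in the two arms; if they are not, the direction is open. The uptake rates and q values in the working are illustrations, not estimates for this trial.

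The documents do not support a claim that uptake is inflated by a particular amount, that one arm is favoured, or that one practice group is affected more. The point is worth acting on because the uptake level feeds the next trial's design and the safeguard is cheap.

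**What to change.** Keep the fixed window from randomisation. In SAP 6.1.1, 6.1.2 and 6.2:

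1. Classify each vaccination in the window by its date against the campaign used to build the patient's eligible list.
2. Count only eligibility-season doses as uptake.
3. Report later-season doses inside the window on a separate line, by arm and practice.
4. Give the any-dose total as a sensitivity analysis.
5. Report the number of in-season days available within the window for each practice.

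The same edit should state one closing day per horizon, since 6.1.1 and 6.2.1 differ (more than 180 v 180), as do 6.1.2 and 6.2.2 (more than 270 v 210).

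The cost is a few sentences and a check on vaccination dates. If no window crosses a season, the season rule changes no result. The downside is that uptake may be lower, and where a season ends before day 180 the effective in-season window is shorter for practices activated later in that season. Item 5 makes this visible.
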